Procedures: All procedures performed at study initiation also will be repeated at the end of the 6 - 28 day cycles of flutamide vs. placebo intervention in PCOS women. The end of treatment fat biopsy will be performed of the opposite side of the lower abdomen than where the first biopsy was taken. In addition, monthly liver function studies will be performed to detect possible elevations of serum transaminase levels above the normal range during flutamide vs. placebo therapy.

Menstrual records and urinary pregnanediol glucuronide (UPDG): Ovulatory frequency will be determined by having subjects keep a daily menstrual record and collect weekly first morning urine samples for UPDG and creatinine assay. Urine samples will be stored for later analysis. Urine samples will be analyzed at the University of Wisconsin-Wisconsin National Primate Research Center for the urinary metabolite of progesterone (urinary pregnanediol glucuronide [UDPG]) and creatinine testing.

Six months following the completion of protocol procedures, participants who received flutamide/placebo will be contacted by phone to check on the status of their health. Subjects will be asked if they have experienced any health problems or have become pregnant since they completed the study procedures.

Daily diaries will include self reporting on taking pills, menstrual flow, symptoms, concomitant medications, exercise patterns, and diet habits.

Quality of life assessments and ovarian size measurements will be conducted at baseline, and at the end of 3 and 6 months of treatment. The PHQ, Beck's Anxiety, Beck's Depression questionnaires will be completed at baseline. The Beck's Depression and Beck's Anxiety will be completed at 3 and 6 month visits. Scoring of the Quality of Life surveys (Beck's anxiety and Beck's depression questionnaires) will be at the time the subject is present for their study visit. If any areas of concern are identified, they will be addressed with the subject before they leave and the appropriate referrals

Revised 3-7-18 UCLA IRB #12-001780 Page 8 of 27

will be made.

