If a woman becomes pregnant while participating in this study she will be excluded from further participation.

Non-English speaking individuals will be excluded from this study. The eligibility criteria includes non-Hispanic Caucasians only so it is assumed that the vast majority of participants will be English speaking. Since PCOS phenotype varies by ethnicity, eligibility was restricted to only one ethnic group in order to control for ethnic variability.

SUBJECT IDENTIFICATION AND RECRUITMENT

Initial contact may be made at the time the patient visits the clinic for non-research related indications. The treating physician, colleague physician, nurse, medical assistant or study coordinator will interface with the potential subject to obtain their consent to be contacted regarding the study. In addition, IRB approved scripts for contact recruitment, responding by e-mail, in person contact or referral contact will be used.

Additionally, patients will be recruited by obtaining a list of possibly eligible patients by extraction of electronic medical records as described in the "Review of Medical Records" section below. After reviewing their charts, verifying eligibility, and obtaining approval from their PCP or GYN provider, patients will be directly contacted by a member of the study team using the IRB approved screening script.

Since potential subjects may contact us directly in response to flyers, ads, etc., we will respond to all inquiries via phone or email as they prefer. If a potential participant contacts us directly by email and wishes more information without phone contact, the consent form will be sent to them via email for their consideration. If they are interested in the study, they will have the option to respond by phone for further screening. The study team will utilize the recruitment script/screening script. The recruitment script/screening script will not be sent via email to potential subjects.

Subjects who have already undergone an OGTT test will be contacted at their next

study visit or by phone to be given the opportunity to undergo FSIGT testing.

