Postmarketing data report the need for hospitalization and rare death events from liver failure in patients receiving flutamide. The flutamide dose chosen for this study is lower than the flutamide dose previously reported to harm the liver, with long-term (>1 year duration) flutamide studies showing no harmful liver effects at a dose of flutamide of 125 mg orally daily. Therefore, we do not anticipate that study participants with PCOS who receive flutamide (125 mg orally daily) in our study are at significant risk for harmful liver toxicity.

Study participants with PCOS who receive flutamide or placebo (125 mg orally daily) will be monitored with monthly blood tests. We will utilize the National Cancer Institute Common Terminology Criteria for Adverse Events (CTCAE) Version 4.0. Should a patient experience any hematologic or non-hematologic toxicity at grade 3 or higher, flutamide/placebo will discontinued and weekly blood tests will be performed until values return to normal.

If a patient experiences an acute life threatening adverse event, we will immediately contact the Investigational Drug Pharmacist and the blind will be broken.

As stated in the consent form, the risks include:

Revised 3-7-18 UCLA IRB #12-001780 Page 18 of 27

The possible risks and/or discomforts associated with the procedures described in this consent form include:

Flutamide:

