Symptoms of liver injury, including loss of appetite, nausea and vomiting, fatigue, stomach or abdominal pain, flu-like symptoms and jaundice (yellowing of the skin or whiteness of the eyes), have occasionally been reported with the use of flutamide. Such liver injury, however, is related to the dose of flutamide and is reversible following discontinuation of the drug. For this reason, the flutamide dose chosen for this study is below the dose previously reported to harm the liver, with long-term (>1 year) flutamide studies showing no harmful liver effects at 125 mg orally on a daily basis. Additional risks of flutamide therapy include anemia, photosensitivity, breast tenderness, retention of fluid, discharge of fluid from your nipples, rash, hypertension, hot flashes, central nervous system reactions, decreased interest in having sexual relations, diarrhea, and anorexia. For these reasons, monthly blood tests will be done to monitor the safety of flutamide and this medication will be discontinued if there are any temporary changes in blood or liver function. Brownish urine also can occur and is due to a metabolite of flutamide.

Placebo Pills

There are no known risks from taking a placebo pill.

Risks of an Ultrasound:

Participants may experience some discomfort from having the ultrasound probe placed in their vagina and moved during the exam.

Ultrasound imaging has been used for over 20 years and has an excellent safety record. It is non-ionizing radiation, so it does not have the same risks as x-rays or other types of ionizing radiation.

Even though there are no known risks of ultrasound imaging, it can produce effects on the body. When ultrasound enters the body, it heats the tissues slightly. In some cases, it can also produce small pockets of gas in body fluids or tissues (cavitation), although this is extremely rare. The long-term effects of tissue heating and cavitation are not known.

Risks of Blood Draw:

Drawing blood may cause temporary pain from the needle stick, bruising or swelling at the site, and rarely, infection or fainting.

Revised 3-7-18 UCLA IRB #12-001780 Page 19 of 27

Risks of Procedure to Remove Fat from Under the Skin:

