As this study involves the use of identifiable, personal information, there is a chance that a loss of confidentiality will occur. The researchers have procedures in place to lessen the possibility of this happening.

Unknown Risks and Discomforts:

The experimental treatments may have side effects that no one knows about yet. The researchers will inform subjects if they learn anything that might make them change

their mind about participating in the study.

POTENTIAL BENEFITS

Society will benefit from the knowlege gained by this study.

PCOS affects at least 7% of the general female population, and these women have an increased risk of diabetes, hypertension and dyslipidemia, infertility, dysfunctional uterine bleeding and endometrial carcinoma. The proposed studies will have the potential benefit of improving our understanding of how altered adipogenesis in PCOS adversely affects metabolic and reproductive function, allowing for the development of newer, and more targeted, therapies. Specifically, clinically relevant knowledge gained by these studies will be a decisive step in improving reproduction in PCOS women and the safety of ovulation-inducing agents when necessary by diminishing the risks of ovarian hyperstimulation syndrome and multiple pregnancy.

DATA AND SAFETY MONITORING PLAN

A physician member of the OB/GYN Department ([name]), who is not affiliated with the study, will monitor the study on a regular basis. In addition, [name] will review on a monthly basis the status of recruitment and the occurrence of any adverse events. If any untoward events occur, necessary systems changes will be promptly instituted.

STOPPING RULES

All Grade 3 toxicities will be immediately evaluated by [name] and [name]. The study will be terminated if two patients experience Grade 3 NCI-defined adverse hepatic events (i.e., serum alkaline phosphatase > 5-20 ULN, alanine aminotransferase > 5-20 ULN, aspartate aminotransferase > 5-20 ULN, total bilirubin > 3-10 ULN) or if one patient experiences a single Grade 4 NCI-defined adverse hepatic event (i.e., serum alkaline phosphatase > 20 ULN, alanine aminotransferase > 20 ULN, aspartate aminotransferase > 20 ULN, total bilirubin > 10 ULN, aspartate aminotransferase > 20 ULN, total bilirubin > 10 ULN).

RULES FOR WITHDRAWING PARTICIPANTS FROM STUDY INTERVENTIONS

Reasons participants may be withdrawn from the study include but are not limited to the following:

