1) Participant chooses for any reason to discontinue her participation in the study.

2) It is deemed by the Principal Investigator that continued participation is not in the best interests of the participant.

3) Blood samples cannot be obtained by a health care provider licensed to perform

phlebotomy..

4) The subject has a persistent adverse reaction to blood sampling, such as dizziness, anxiety or pain.

5) During the frequently sampled glucose tolerance test (FSIGT), the subject experiences nervousness, irritability, headache, pale and clammy skin or excessive sweating, which are not promptly reversed according to the protocol stated on the signed physician's orders.

6) During the entire duration of procedures involving blood draws, nursing staff will be present to monitor for any of the above adverse symptoms. If significant symptoms of hypoglycemia develop, oral or intravenous glucose will be administered.

7) The surgeon performing the removal of the fat deems the fat acquisition procedure unsafe due to pre-existing anatomic distortion of the abdomen, or to unrelated complications arising during the procedure. Because a low yield of adipocytes may result from small adipose sampling, and poor sample handling or cellular fragility, only an experienced surgeon (Drs. [name] or [name]) will perform the subcutaneous fat biopsy procedure.

8) Elevation in liver function studies above the normal range.

9) If the participant becomes pregnant.

10) Noncompliance

11) Subjects will be monitored for hypertension. If a subject has persistent increase in diastolic blood pressure of 20 mm Hg or more, or if a previously normotensive subject experiences persistent increase in blood pressure to > 150/100, flutamide/placebo will be discontinued and the subject will be withdrawn from study treatment.

FINANCIAL OBLIGATIONS

Neither the subject nor their insurance carrier will be charged for their participation in this study.

Control participants may receive up to \$300 for their participation in this study and PCOS participants may receive up to \$840.

Participants will be reimbursed for their parking expenses. Meal vouchers will be provided during the FSH visit.

STATISTICAL CONSIDERATIONS

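### The point at which a woman must stop flutamide/placebo is set at grade 3 or higher in one place and lower in the consent wording, and the withdrawal list does not settle it

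*Combined protocol and SAP*

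**What the plan says.** Three places govern when an individual woman stops study drug.

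- **Potential Risks, toxicity instruction.** After adopting CTCAE version 4.0, the protocol says: "Should a patient experience any hematologic or non-hematologic toxicity at grade 3 or higher, flutamide/placebo will discontinued". Weekly blood tests then follow until values normalise.
- **Potential Risks, flutamide paragraph.** This text is introduced as coming from the consent form. It says that "this medication will be discontinued if there are any temporary changes in blood or liver function". It gives neither a grade nor a limit.
- **Rules for Withdrawing Participants from Study Interventions, item 8.** The entry is "Elevation in liver function studies above the normal range". The list is introduced with "Reasons participants may be withdrawn from the study include but are not limited to the following".

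Two other places give context. Stopping Rules, which govern termination of the whole study, spell out hepatic grade 3 as "serum alkaline phosphatase > 5-20 ULN, alanine aminotransferase > 5-20 ULN, aspartate aminotransferase > 5-20 ULN, total bilirubin > 3-10 ULN". Aim 2, Procedures, says that "monthly liver function studies will be performed to detect possible elevations of serum transaminase levels above the normal range", but attaches no action to a positive finding.

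**The concern.** A rule for stopping a drug with known hepatic toxicity should read the same wherever it appears, and the consent should tell a woman what staff will actually do. Here the operational instruction sets a high bar, the consent promises a much lower one, and the withdrawal list sits near the lower one without clear force. Nothing says which governs.

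Two things are at stake. The first is consistent handling of mild and moderate liver-test elevations. The protocol itself acknowledges post-marketing reports of hospital admission, and rarely death, from hepatic failure with flutamide. The second is the accuracy of the consent. No endpoint, sample size or power calculation depends on this point.

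**Working it through.** The plan gives no figure to reproduce. The check is to set the rules side by side, using the protocol's own grade 3 limits.

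**Inputs**
- Lower limits of hepatic grade 3, from Stopping Rules: 5 ULN for ALT, AST and alkaline phosphatase; 3 ULN for bilirubin.
- Lower trigger, from item 8: above normal, taken here as above 1 ULN. For transaminases, Aim 2, Procedures, uses the same standard for monitoring. For alkaline phosphatase and bilirubin the 1 ULN bound rests on item 8 alone, assuming that its undefined term for liver tests includes them.
- Consent wording: no numerical limit.

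**Comparison**

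| Finding | Toxicity instruction | Consent wording | Item 8 |
|---|---|---|---|
| ALT, AST or alkaline phosphatase above 1 and up to 5 ULN; bilirubin above 1 and up to 3 ULN | No requirement | Drug is stopped | May be withdrawn |
| ALT, AST or alkaline phosphatase above 5 ULN; bilirubin above 3 ULN | Drug is stopped | Drug is stopped | May be withdrawn |
| Blood-count change below grade 3 | No requirement | Drug is stopped | Not covered |

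The first and third rows are where the rules part. Take a woman with ALT at 4 ULN. Since 1 < 4 ≤ 5, the toxicity instruction asks for nothing, her consent says drug will be stopped, and item 8 lists her as someone who may be withdrawn.

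**Force of item 8.** The list's introduction is permissive, yet some of its entries are mandatory. Pregnancy is mandatory because Exclusion Criteria say "If a woman becomes pregnant while participating in this study she will be excluded from further participation". The blood-pressure criterion in item 11 is mandatory because it carries its own wording: "flutamide/placebo will be discontinued and the subject will be withdrawn from study treatment". Item 8 has neither kind of support. The introductory wording therefore does not settle every item, but nothing in the text makes item 8 mandatory either.

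The firm mismatch is thus between the toxicity instruction and the consent wording. Both use mandatory language, at different levels. In the third row no interval can be stated, because the consent wording gives no limit for blood values.

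**The case against.** The strongest reply is that the rules do not collide. The toxicity instruction can be read as a general mandatory floor for any toxicity, with item 8 as a lower, liver-specific reason left to judgement. The consent sentence is lay wording and errs on the side of caution. The consent pages are not in the copy reviewed, so the form may say more. Harm would require staff to follow the toxicity instruction and overlook the withdrawal list. Safeguards also exist: monthly panels, discontinuation at grade 3, monitoring by a physician outside the study, and a study-level hepatic stopping rule. The protocol adds that the dose is below that reported to harm the liver, and that studies beyond a year at 125 mg daily showed no hepatic harm.

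Much of this stands. A reader might infer an outright contradiction, but stopping at the lowest trigger satisfies all three texts, and the toxicity instruction does not order continuation below grade 3. A reader might also infer that item 8 already obliges withdrawal at any value above normal; as shown above, its wording does not go that far. Nor do the documents support calling this a missing safeguard.

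What the reply does not remove is the consent sentence. The two-tier reading is plausible, but the protocol never states it. Even under that reading, a woman between normal and grade 3 might be kept on drug at the investigator's discretion, whereas the protocol's own rendering of the consent says drug will be stopped.

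**Conclusion.** The point holds as an inconsistency in a participant-safety rule and in the consent wording, and should be fixed. The mandatory protocol trigger and the mandatory consent trigger differ for ALT, AST and alkaline phosphatase from above 1 to 5 ULN, for bilirubin from above 1 to 3 ULN, and for blood changes below grade 3 over a range that cannot be stated. Item 8 points toward the lower hepatic trigger but, as written, does not require it.

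This rests on two assumptions: that above normal means above 1 ULN, and that item 8's liver tests include alkaline phosphatase and bilirubin. It also relies on the protocol's reproduction of the consent text.

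A reader might want a count of women or of panels affected. The documents give no rate of elevations below grade 3. The 36 planned PCOS completers are not the right base either, because the rule applies to every treated woman, including those who stop early. No such figure is offered.

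**What to change.** State one individual rule in the same terms in the toxicity instruction, the consent wording and item 8.

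- **Using the protocol's own item 8 criterion:** flutamide/placebo is discontinued for any liver test above normal, and for any other toxicity at grade 3 or higher. Give item 8 explicit mandatory wording, as item 11 already has.
- **If item 8 is meant to be discretionary:** say so. Discontinuation is then at the investigator's discretion for liver tests above normal and mandatory at grade 3 or higher, and the consent describes exactly that.

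Under either option, replace the consent sentence about any temporary change, which read literally would stop drug for blood fluctuations that no other part of the protocol treats as a reason. List the liver tests meant in item 8. Leave the study-level stopping rule as it is; it is not in conflict, although earlier individual stopping could make it less likely to be reached.

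The cost is a protocol and consent wording amendment, with notice to women currently on study drug. The first option may bring some more discontinuations for mild elevations than the toxicity instruction alone, in a number the documents do not allow to be computed. It also leaves a follow-up choice to state. Weekly retesting is now tied to grade 3 or higher, so a woman stopped at a lower value has a specified panel only 30 days after her last pill. Keeping that adds no procedure; extending weekly tests to her would add blood draws.

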The study procedures will take place at UCLA Westwood Campus in the 200 and 300 Medical Plaza Buildings, the Clinical Translational Research Center, Ronald Reagan Medical Center, and/or Room 22-265 in the Center for Health Sciences.

Before subjects begin the study:

Before they begin the study, subjects will need to agree to use a non-hormone type of

Revised 3-7-18 UCLA IRB #12-001780 Page 12 of 27

birth control for the duration of their participation in this study. If subjects have not undergone permanent sterilization, examples of acceptable types of birth control are an IUD (without hormones) or spermicidal jelly in combination with a diaphragm or condoms.

During the study:

If subjects take part in this study, the researcher(s) will ask them to do the following:

All Study Participants

Initial Visit

• The consent form will be reviewed with the subject and anyone they wish to have present. If they choose to participate, they will sign the consent form and HIPAA Authorization form. Subjects will be given a copy for their records.

The doctor will ask questions regarding their past medical history, family medical history, and lifestyle to determine if they are eligible to participate in this study.
If subjects are not eligible to participate in this study, no further study related office visits or procedures will be performed and they will receive \$10 for their time
If subjects are eligible to participate, they will undergo the following:

- Physical Exam
- An assessment of their skin
- Height, weight, waist and hip measurements
- Transvaginal ultrasound of their ovaries
- Blood tests approximately 1 teaspoon (6 ml) of blood will be drawn from their vein. All of the blood samples in this study will be used to detect any abnormal hormone levels. A pregnancy test will also be performed.
- Complete questionnaires regarding their feelings about various areas of their health, quality their life, and family history of PCOS and/or diabetes. Subjects have the right to refuse to answer any questions that they do not wish to answer.
- \circ Whether subjects are eligible or not, they will be paid \$20 for completing this visit.
 - It is estimated that this visit will take approximately 2 hours.

Women with and without PCOS

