• The first blood draw will be sent to the laboratory for an immediate test of their progesterone level which indicates whether or not they are ovulating. If the progesterone test indicates that they are ovulating, the FSH test will not be able to be performed that day and will need to be rescheduled. If the test cannot be performed, they will be paid \$10 for this visit and another appointment will be scheduled.

• It will be necessary for them to stay at UCLA Medical Center in the Clinical Translational Research Center, which is located in the Center for Health Sciences building for approximately 26 hours in order to complete this test. Food will be provided to them during the testing.

• Approximately 1-2 tablespoons (21 mL) of blood will be drawn from their vein.

If subjects have PCOS, an additional 4 mL (approximately 1 teaspoon) of blood will be drawn for a complete blood count and comprehensive metabolic panel in order to assure that there are no abnormalities in these blood values before they begin taking flutamide or placebo.

Since some of the blood tests to confirm hormonal levels are timed around different phases of the menstrual cycle and menstrual cycles vary, it is possible some of the blood tests described above will need to be repeated. The Frequently Sampled

Intravenous Glucose Tolerance Test and the Follicle Stimulating Hormone Test will only be performed as described above.

Subjects will be paid \$280 once they have completed the FSIGT, DXA, MRI, Fat Removal, and FSH stimulation visits. If they report to UCLA for a study visit and their blood tests indicate that they are not in the desired part of their menstrual cycle for a particular test, they will be compensated an additional \$10 and the visit will be rescheduled. Participants will be asked to complete a form so that a check can be mailed to them within 2 months.

Women who do not have PCOS will conclude their participation in this study at this point. No further procedures for this study will be conducted.

Women with PCOS will continue participation as described below.

Women with PCOS will be asked to do the following:

• Take one pill (either placebo or flutamide) each morning before breakfast for 6 complete 28 day cycles. The drug flutamide has not been approved by the FDA for use in women or for the treatment of PCOS.

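### The flutamide risk wording taken from the consent form calls liver injury reversible without qualification, although the protocol itself reports rare deaths from liver failure; the sentence is over-broad and should be qualified

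*Combined protocol and SAP*

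**What the plan says.** The Potential Risks section of the combined protocol and SAP opens in the protocol's own voice: "Postmarketing data report the need for hospitalization and rare death events from liver failure in patients receiving flutamide". It then gives the dose rationale, "The flutamide dose chosen for this study is lower than the flutamide dose previously reported to harm the liver", citing studies of more than one year without liver harm at 125 mg daily.

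The section next turns to participant wording with the phrase "As stated in the consent form, the risks include". Under the Flutamide subheading, that wording begins with "Symptoms of liver injury, including loss of appetite, nausea and vomiting, fatigue, stomach or abdominal pain, flu-like symptoms and jaundice", and says these have occasionally been seen with the drug. It continues: "Such liver injury, however, is related to the dose of flutamide and is reversible following discontinuation of the drug". The dose rationale follows in nearly the same terms ("the flutamide dose chosen for this study is below the dose previously reported to harm the liver"). The paragraph ends with monthly blood tests and a commitment to stop the drug if blood or liver results change, calling such changes temporary.

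**The concern.** Two adjacent parts of one section describe the outcome of flutamide liver injury differently. The part written for the protocol reader includes hospitalization and death from liver failure. The part presented as what participants are told says only that the injury reverses when the drug is stopped.

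What is at stake is the accuracy of what women are told. Participants are aged 18 to 35, and the Procedures section says of the study drug: "The drug flutamide has not been approved by the FDA for use in women or for the treatment of PCOS". At the Initial Visit, "The consent form will be reviewed with the subject" before she signs. Death from liver failure is the only fatal flutamide outcome that the protocol names, so an unqualified reassurance on this point matters more than one on a lesser side effect.

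**Working it through.** No arithmetic applies and there is no plan figure to reproduce. The check is a comparison of wording.

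1. **Scope of the participant sentence.** The word *such* refers to the injury whose symptoms were just listed. The list runs up to jaundice, is tied to flutamide use in general rather than to 125 mg, and does not set severe injury apart. The statement carries one condition (the drug is stopped) and no hedge such as *usually* or *in most cases*.

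2. **Scope of the protocol sentence.** It concerns patients receiving flutamide and names hospitalization and rare deaths from liver failure. It gives no dose, no duration of treatment, and no timing of the liver failure relative to stopping.

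3. **Can both be true?** Strictly, yes. The participant sentence says that injury reverses once the drug is stopped. The protocol sentence says that some patients died of liver failure. A contradiction would need a case in which the drug was stopped and the injury did not reverse, and the documents report no such case. The protocol sentence does establish that flutamide liver injury has sometimes ended in hospitalization or death. A lay reader of the participant sentence would not learn of that possibility.

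4. **Is it qualified elsewhere in the reproduced text?** From the Flutamide subheading to Unknown Risks and Discomforts:
   - Wording on how liver injury or liver changes end: 2 places (the reversibility sentence, and the description of liver changes as temporary). Both reassure.
   - Mentions of liver failure: 0. Hospitalization: 0. Death: 0.
   - Rare events are disclosed for other procedures: fainting, possibly with convulsions, from the fat biopsy, and tissue cavitation from ultrasound. Rarity alone was therefore not a reason for silence in this text.

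5. **Does the dose rationale correct it?** No. A dose below the one known to harm the liver bears on how likely injury is in this trial. It does not bear on whether a general statement about how the injury ends is accurate.

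6. **Do the safeguards correct it?** No. They are monthly liver tests (Aim 2, Procedures; Potential Risks), stopping the drug at Grade 3 toxicity or higher (Potential Risks), liver tests above normal as a reason for withdrawal (Rules for Withdrawing Participants), and termination at two Grade 3 hepatic events or one Grade 4 (Stopping Rules). They limit physical risk and make early stopping likely, but they do not change what the sentence says.

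**The case against.** The strongest reply is that no contradiction is shown. The claim of reversibility is conditional on stopping, and the deaths are reported without saying whether or when the drug was stopped; they could all be late-recognised cases or cases in which the drug was continued. *Such* may also mean only the symptomatic injury just listed. The first part stands in full and limits the conclusion to over-breadth. The second is a possible reading, but a participant cannot be expected to find an exception that the text does not state.

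A further reply is that the full consent form is not available for review. The phrase that introduces the excerpt does not claim completeness, so the form may mention liver failure elsewhere. That stands too: the zero counts above describe the excerpt, not everything participants were told.

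Three stronger readings are tempting, and the documents support none of them:

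- **That the consent form conceals fatal liver failure.** Only an excerpt can be seen.
- **That the protocol's Grade 3 and Grade 4 hepatic rules show that it regards the injury as irreversible.** Those grades are laboratory thresholds. The protocol plans weekly tests after Grade 3 or higher until values normalise, which fits an expectation of recovery.
- **That participants are physically under-protected.** The monitoring and withdrawal rules argue against this, and they favour the early stopping on which reversibility depends.

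**Conclusion.** The point holds as a minor participant-information correction. In the reproduced risk text, one sentence states reversibility without qualification and nothing nearby corrects it, while the same section reports hospitalization and rare deaths from liver failure. The sentence is over-broad and over-reassuring. A reader might infer that it is false; the documents do not go that far, because they do not show that any injury persisted after stopping.

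The size is one sentence. The documents give no incidence of liver failure at 125 mg or at any other dose, so no harm rate is offered.

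The conclusion assumes that the excerpt matches the consent form, as the protocol states. It does not depend on what the rest of the form says: if liver failure is disclosed there, the reversibility claim would still need a qualifier, though the added disclosure would not be needed.

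**What to change.** In the Flutamide paragraph of Potential Risks and the matching consent wording, replace the sentence with, for example: *This liver injury is related to the flutamide dose and can be reversible if the drug is stopped, but hospitalization and rare deaths from liver failure have been reported in patients taking flutamide.* Keep the existing statement on the 125 mg dose and the studies of more than one year directly after it, so that the added fact is read in proportion. *Usually reversible* would be acceptable only if the sponsor's source supports that frequency.

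First check the full consent form. If it already discloses liver failure, only the reversibility claim needs qualifying.

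The cost is one wording amendment to the protocol and consent form, plus informing women still on treatment. The documents do not give enrolment status at this March 2018 version, so that number is unknown. A few women may decline; this is a judgement, not a figure from the documents. Endpoints, analysis, sample size and monitoring do not change.
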